### 8. OUTPUT PRESENTATIONS

Appendix 1 shows conventions for presentation of data in outputs.

The templates provided with this SAP describe the presentations for this study and therefore the format and content of the summary tables, figures, and listings to be provided by IQVIA Biostatistics.

Document: \\ieedc-vnasc01\BIOSdata\Menarini\NebZof\KZA41200\Biostatistics\Documentation\SAP

Author: [name] Version Number: Final V1.0

Version Date: [14Dec2021]

Template No.: CS\_TP\_BS016 Revision 6 Reference: CS\_WI\_BS005

Page 22 of 37

#### 9. DISPOSITION AND WITHDRAWALS

All patients who provide informed consent will be accounted for in this study.

### 9.1. DISPOSITION

All patients who provided informed consent will be considered for this study. Patient disposition and withdrawals, and reasons for exclusion from each analysis population, including inclusion and exclusion criteria will be presented for the ENR population.

#### 9.2. PROTOCOL DEVIATIONS

All protocol deviations (PD) will be discussed and reviewed on a case-by-case basis before the DBL. All PDs authorized by Sponsor will be documented.

Individual PDs will be presented in a data listing. The number and percentage of patients with PDs will be summarized by deviation on ENR population. Additional Major and Minor PDs may be identified during data review and will be reflected in the Table and Listing as appropriate.

All PDs will be recorded and classified in Clinical Trial Management System (CTMS).

#### **9.3.** COVID-19 IMPACT

The impact of COVID-19 on study related procedures are collected on 'COVID-19 Impact Form' in eCRF. Impact information will be presented in a summary table and a data listing.

### 10. DEMOGRAPHIC AND OTHER BASELINE CHARACTERISTICS

Demographic data and other baseline characteristics will be presented for the ENR. No statistical testing will be carried out for demographic or other baseline characteristics. The following demographic and other baseline characteristics will be reported for this study

- Age (years)
- Sex
- Race
- Childbearing potential

Document: \\ieedc-vnasc01\BIOSdata\Menarini\NebZof\KZA41200\Biostatistics\Documentation\SAP

Author: [name] Version Number: Final V1.0

Version Date: [14Dec2021]

Template No.: CS\_TP\_BS016 Revision 6 Reference: CS\_WI\_BS005

Page 23 of 37

- Weight (kg)
- Height (cm)

### **10.1. DERIVATIONS**

• BMI  $(kg/m^2)$  = weight (kg)/ height  $(m)^2$ 

### 11. MEDICAL HISTORY

Medical History information will be presented for the ENR.

- Medical History data captured on eCRF will be coded using Medical Dictionary for Regulatory Activities (MedDRA, Version 23.1 or latest) dictionary
  - Medical History conditions are defined as those conditions which stop prior to or at Screening.
  - Presented by SOC and PT.

### 12. CONCURRENT DISEASES

Concurrent Diseases will be presented for the SAF by combination therapy.

- Concurrent Diseases will be coded using Medical Dictionary for Regulatory Activities (MedDRA, Version 23.1) dictionary
  - Concurrent Diseases are conditions started prior to or at Screening and are ongoing at the date of Screening.
  - Presented by SOC and PT.
  - Concurrent Diseases conditions are defined as those conditions recorded in the eCRF form "Concurrent Diseases and Medical Conditions".

#### 13. MEDICATIONS

Medications will be presented for the SAF and coded using WHO Drug dictionary Version 01SEP2020 or latest. See Appendix 2 for handling of partial dates for medications, in the case where it is not possible to define a medication as prior, concomitant, the medication will be classified by the worst case, i.e. concomitant.

Frequency tabulations will be presented for prior and concomitant medications by primary therapeutic subgroup (3rd

Document: \\ieedc-vnasc01\BIOSdata\Menarini\NebZof\KZA41200\Biostatistics\Documentation\SAP

Author: [name] Version Number: Final V1.0

Version Date: [14Dec2021]

Template No.: CS\_TP\_BS016 Revision 6 Reference: CS\_WI\_BS005

Page 24 of 37

level ATC code) and preferred name.

- 'Prior' medications are medications which started and stopped prior to the first dose of study medication.
- 'Concomitant' medications are medications which:
  - o started prior to, on or after the first dose of study medication,
  - AND ended on or after the date of first dose of study medication or were ongoing at the end of the study.

### 14. STUDY MEDICATION EXPOSURE

Exposure to study medication for both Monotherapy and Combination therapy in days will be presented for the ENR and SAF respectively.

The date of first study medication administration will be taken from the eCRF "Exposure" form. The date of last study medication will be taken from the eCRF "End of Study Treatment" form.

Interruptions, compliance, and dose changes are not taken into account for duration of exposure.

#### 14.1. DERIVATIONS

Duration of exposure (days) = date of last study medication administration – date of first study medication administration + 1.

#### 15. STUDY MEDICATION COMPLIANCE

Compliance to study medication will be presented for the ENR and SAF.

A table consisting of summary statistics for percent compliance along with the number and percent of patients with compliance in each of the following groups:

Low: percentage of compliance <80%

Normal: percentage of compliance =>80% - <=120%

High: percentage of compliance >120%

on ENR population for Monotherapy and SAF population for Combination therapy.

A listing of drug accountability will be presented on ENR population by phase to account for all drug distributed to each patient, including the box number, total number tablets dispensed, returned, consumed, lost (if any), percentage compliance and compliant (yes/no).

Document: \\ieedc-vnasc01\BIOSdata\Menarini\NebZof\KZA41200\Biostatistics\Documentation\SAP

Author: [name] Version Number: Final V1.0

Version Date: [14Dec2021]

Template No.: CS\_TP\_BS016 Revision 6 Reference: CS\_WI\_BS005

Page 25 of 37

#### 15.1. DERIVATIONS

Compliance with study medication—based on the drug accountability data will be calculated as the number of tablets taken (total dispensed – total returned) divided by the prescribed number of tablets expressed as a percentage, see calculations below.

Mono/Combination Therapy and overall Compliance with study drug based on the drug accountability data will be calculated as the number of tablets taken x 100 / expected number of tablets which should have been taken expressed as a percentage.

For patients who permanently stop the study medication, the expected number of tablets will be calculated up-to the date of study withdrawal.

### 16. EFFICACY OUTCOMES

#### 16.1. PRIMARY EFFICACY

#### 16.1.1. PRIMARY EFFICACY VARIABLE & DERIVATION

The primary efficacy variable is Change in mean sitting DBP between Week 0 (Visit 2) and Week 8 (Visit 3).

#### 16.1.2. MISSING DATA METHODS FOR PRIMARY EFFICACY VARIABLE(S)

Not Applicable.

#### 16.1.3. PRIMARY ANALYSIS OF PRIMARY EFFICACY VARIABLE

The primary objective of this study is to test the hypothesis that

- H0: There is no change in the sitting DBP prior or post combination therapy
- H1: There is a difference in the sitting DBP prior or post combination therapy.

The primary efficacy analysis will be performed for the ITT population. The above hypothesis will be tested as following-

• Change from baseline in sitting DBP from prior and post combination therapy will be compared using paired t-test. The p-value will be presented using paired t-test.

Document: \\ieedc-vnasc01\BIOSdata\Menarini\NebZof\KZA41200\Biostatistics\Documentation\SAP

Author: [name] Version Number: Final V1.0

Version Date: [14Dec2021]

Template No.: CS\_TP\_BS016 Revision 6 Reference: CS\_WI\_BS005

Page 26 of 37

- The primary endpoint will be presented in a descriptive manner using n, mean, median, SD, Q1, Q3, minimum and maximum.
- Assumption of normality will be investigated using Wilk-Shapiro test. If violation is observed, then paired ttest will be replaced by Wilcoxon signed rank test.

#### 16.1.4. SENSITIVITY ANALYSIS OF PRIMARY EFFICACY VARIABLE(S)

The primary sensitivity analysis will be conducted using the PP population.

### 16.2. SECONDARY EFFICACY

#### 16.2.1. SECONDARY EFFICACY VARIABLES & DERIVATIONS

• Change in mean sitting SBP

Change in mean sitting SBP between Week 0 (Visit 2) and Week 8 (Visit 3)

Number and proportion of patients achieving the BP goal

Number and proportion of patients achieving the BP goal (sitting BP  $\leq$ 130/80 mmHg) at Week 0 (Visit 2) and Week 8 (Visit 3).

#### 16.2.2. ANALYSIS OF SECONDARY EFFICACY VARIABLES

Secondary efficacy variables will be summarized in a descriptive manner using ITT population.

• Change in mean sitting SBP between Week 0 (Visit 2) and Week 8 (Visit 3):

Change from baseline in sitting SBP from prior and post combination therapy will be compared using paired t-test. The p-value will be presented using a paired t-test comparing mean at baseline and mean at Week 8. The secondary endpoint will be presented in a descriptive manner using n, mean, median, SD, Q1, Q3, and minimum and maximum.

Assumption of normality will be investigated using Wilk-Shapiro test. If violation is observed, then paired t-test will be replaced by Wilcoxon signed rank test.

• The number of patients achieving BP goal (sitting BP ≤130/80 mmHg) will be summarized for Visit 2 and Visit 3, along with percentage. A p-value using exact McNemar's test will be presented to compare the proportion of patients achieving the BP goal (sitting BP ≤130/80 mmHg) between Visit 2 and Visit 3.

Document: \\ieedc-vnasc01\BIOSdata\Menarini\NebZof\KZA41200\Biostatistics\Documentation\SAP

Author: [name] Version Number: Final V1.0

Version Date: [14Dec2021]

Template No.: CS\_TP\_BS016 Revision 6 Reference: CS\_WI\_BS005

Page 27 of 37

### 16.2.3. SENSITIVITY ANALYSIS OF SECONDARY EFFICACY VARIABLE(S)

The secondary sensitivity analysis will be conducted using the PP population for change in mean sitting SBP between Week 0 (Visit 2) and Week 8 (Visit 3).

#### 16.3. EXPLORATORY EFFICACY

#### 16.3.1. EXPLORATORY EFFICACY VARIABLES & DERIVATIONS

- Change in mean sitting SBP and DBP between Visit 1 and Visit 2 in the group of patients on ZOF 30 mg and NEB 5 mg and in the group of patients switched to ZOF 30 mg or NEB 5 mg from any other ACE-I and BB
- Change in mean sitting SBP and DBP between Visit 1 and Visit 3 in the group of patients on ZOF 30 mg and NEB 5 mg or in the group of patients switched to ZOF 30 mg or NEB 5 mg from any other ACE-i and BB
- Number and proportion of patients in the group of patients on ZOF 30 and NEB 5 mg and in the group of patients switched to ZOF 30 mg or NEB 5 mg from any other ACE-I and BB achieving the BP goal (sitting BP ≤130/80 mmHg) at Visit 2 and Visit 3
- Number and proportion of patients on combination therapy, divided into subgroups specified under section 7.5, achieving the BP goal (sitting BP ≤130/80 mmHg) at Visit 2 and Visit 3

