#### **Protocol Template**

Sponsor: Menarini Pharmaceutical Study Code: MEIN/19/ZoNe-HYP/001

Protocol Version\_1 of 16/07/2020

The subjects meeting all inclusion criteria and none of the exclusion criteria will enter into the run-in period on the same day and will receive monotherapy of ZOF 30 mg or NEB 5 mg.

- Patients who are already on therapy with ZOF 30 mg or NEB 5 mg will be provided with the same medication
- Patients taking any other BBs will be provided with NEB 5 mg, and patients taking any other ACE-i will be provided with ZOF 30 mg

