#### 14.2 Determination of Sample Size

Considering a screen failure and a drop-out rate of 25% from Visit 1 and Visit 3, the number of patients to be screened is 290. Two-hundred and sixteen with uncontrolled hypertension, are planned to be included at Screening in the assessment period lasting for 8 weeks. A total sample size of 216 patients is required to achieve 90% power at 5% significance level assuming a difference in mean DBP from baseline to 8 weeks of 4 mmHg and a standard deviation (SD) for this difference of 10 mmHg. The mean change in DBP for null hypothesis is set at 2 mmHg.

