### 7.5. EXAMINATION OF SUBGROUPS

Subgroup analyses will be conducted as stated in the exploratory analysis sections. It should be noted that the study was not designed to detect treatment differences with high statistical power within subgroups.

The following subgroups will be assessed and described within the exploratory analysis sections on ITT and PP populations.

- Country/Site
- Age (<40 years and  $\ge40$  years)
- Gender (Male, Female, Other)
- Hypertension grade at screening (grade 1 and grade 2)
- Presence of diabetes (patients with or without diabetes)
- Presence of hypercholesterolemia (patients with or without hypercholesterolemia)
- Screening therapy (ACE-i, Beta blocker)
- Run-in period therapy (Monotherapies of ZOF 30 mg or NEB 5 mg)

Hypertension grade at screening is derived as follows;

- Grade  $1 140 \le SBP \le 160$  or  $90 \le DBP \le 100$
- Grade  $2 160 \le SBP \le 180$  or  $100 \le DBP \le 110$

Patients with presence of diabetes and hypercholesterolemia will be identified from the medical history data using the preferred terms. Presence of diabetes can be identified with the preferred terms "Diabetes mellitus" Or "Type 2 diabetes mellitus" and hypercholesterolemia with "Dyslipidaemia" or "Hypercholesterolaemia" or "Hyperlipidaemia". Patients under ACE-i and beta blocker can be identified from the concomitant medication data with anatomical therapeutic chemical (ATC) class "Ace inhibitors, plain" and "Beta blocking agents, selective" respectively.

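### The Week 0 to Week 8 BP change is not planned by continued versus switched at Visit 1, and the screening-therapy subgroup rule omits some beta-blocker patients

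*SAP*

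**What the plan says.** SAP 16.1.1: "The primary efficacy variable is Change in mean sitting DBP between Week 0 (Visit 2) and Week 8 (Visit 3"). SAP 16.1.3 and 16.2.2 analyse DBP and SBP over this interval in all combination patients together, and SAP 7.1 rules out covariate adjustment.

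Two kinds of patient reach Week 0. Those on NEB 5 mg or ZOF 30 mg at Visit 1 continue. The others are moved to the study drug of their class. Protocol 7.1 states this for beta blockers ("Patients taking any other BBs will be provided with NEB 5 mg") and does the same for ACE inhibitors with ZOF 30 mg.

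The exploratory objective in SAP 2.3 names these two groups and asks for efficacy at different time points. SAP 16.3.1 gives the split three outputs: the Visit 1 to Visit 2 change, the Visit 1 to Visit 3 change ("Change in mean sitting SBP and DBP between Visit 1 and Visit 3 in the group of patients"), and the BP goal at Visits 2 and 3.

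SAP 7.5 lists the subgroup "Screening therapy (ACE-i, Beta blocker"), which is also in Protocol 14.5.6. SAP 7.5 finds beta-blocker patients in the concomitant medication data through the ATC class "Beta blocking agents, selective". SAP 16.3.2 applies the 7.5 subgroups to the BP goal only. SAP 13 classes medication as follows: "Prior' medications are medications which started and stopped prior to the first dose of study medication".

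**The concern.** A switcher's Week 0 baseline is taken 4 weeks ± 2 days (26 to 30 days) after a change of drug, while a continuer had no drug change at Visit 1. There is no control arm. If BP were still moving because of the switch, up or down, that movement would be part of the Week 0 to Week 8 change and would be read as effect of the combination. The grouping needed to look at this is already defined and the readings are collected, but the plan leaves out the one interval that starts when the combination starts. For switchers, the Visit 1 to Visit 3 change mixes the switch with the combination.

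The second problem needs no assumption about drift. A rule limited to selective agents cannot find patients on other classes of beta blocker, so they drop out of the subgroup or are left unclassified.

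**Working it through.** **1. The plan's own figure.** Protocol 14.2: "A total sample size of 216 patients is required to achieve 90% power at 5% significance level". The other inputs given there are a mean DBP change of 4 mmHg, an SD of 10 and a null value of 2 mmHg.

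n = (SD × (z_alpha + z_power) / (4 − 2))²

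- One-sided 5%: (10 × (1.645 + 1.282) / 2)² = 214.1. The exact t calculation gives 216, with power 90.1%, so 216 is reproduced.
- Two-sided 5%, the SAP 6.5 default: (10 × (1.960 + 1.282) / 2)² = 262.7. The exact t calculation gives 265, and power at 216 is 83.3%.

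The sidedness is a separate matter. Only N = 216, SD 10 and the 2 mmHg margin are used below.

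**2. What is planned by continued/switched.**

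| Output | Planned by continued/switched? |
|---|---|
| SBP/DBP change, Visit 1 to 2 | Yes (SAP 16.3.1) |
| SBP/DBP change, Visit 1 to 3 | Yes (SAP 16.3.1) |
| BP goal, Visits 2 and 3 | Yes (SAP 16.3.1) |
| SBP/DBP change, Week 0 to 8 | No |

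Reading Protocol 14.5.6 as applying its subgroups to the primary endpoint would not close the gap, because none of them separates continued from switched. Screening therapy is by design the same partition as run-in therapy: ACE inhibitor goes with ZOF, beta blocker with NEB.

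**3. Possible shift in the pooled mean.** Shift = share switched × residual change after Week 0. Both inputs are assumptions.

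| Residual fall | 25% switched | 50% | 75% |
|---|---|---|---|
| 0 mmHg | 0 | 0 | 0 |
| 1 mmHg | 0.25 | 0.5 | 0.75 |
| 2 mmHg | 0.5 | 1.0 | 1.5 |

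A residual rise gives the same figures with the opposite sign. If the true change equals the null value tested, with n = 216 and SD 10, a shift of 0.5, 1.0 or 1.5 mmHg raises two-sided rejection from 5% to 11%, 31% or 59%.

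**4. Precision of the missing table.** Half-width per group = t(0.975, n − 1) × 10 / √n. For the difference it is t(0.975, 214) × 10 × √(1/n1 + 1/n2).

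| Split of 216 | Per group | Difference | Difference detectable, 80% power |
|---|---|---|---|
| 108 / 108 | ±1.91 | ±2.68 | 3.8 mmHg |
| 54 / 162 | ±2.73 / ±1.55 | ±3.10 | 4.4 mmHg |

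The pooled half-width is ±1.34 mmHg.

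**5. Can it be recovered by subtraction?** (Visit 3 − Visit 1) − (Visit 2 − Visit 1) = Visit 3 − Visit 2. For group means this is exact only if both changes use the same patients. Protocol 14.4 assigns these variables to the Enrolled population, whereas Protocol 14.5.5 and SAP 16.3.2 assign them to the safety population. In the Enrolled population, the Visit 1 to 2 change includes patients withdrawn at Visit 2 because BP was controlled. Visit 3 may also be missing. The SD and interval cannot be obtained from the two summaries.

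**6. The subgroup rule.** Eligibility (Protocol 8.1.1, criterion 1) is monotherapy with an ACE inhibitor or a beta blocker, with no subclass restriction. The SAP 7.5 class is restricted to selective agents, so the rule is narrower than the population it should classify.

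**The case against.** A reader might infer that a still-developing response to the switch is being counted as combination effect. The documents do not support that. Nothing in them says BP is unsettled after 4 weeks, the objectives treat at least 4 weeks of monotherapy as sufficient, and neither drift nor the share of switchers is given. With no drift there is no bias.

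Nor does the missing table cause the mixing. The uncontrolled before-after design does, and a split leaves the primary estimate unchanged. The table is also too imprecise to confirm a drift of 1 to 2 mmHg: at 108/108, power for a 2 mmHg difference is about 31%. Both objections stand and limit the point to a descriptive addition.

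Continuers might be taken as a clean benchmark. They are not. They share regression to the mean after a BP entry threshold, open-label conditions, and diet and exercise counselling. The one-month rule covers any ACE inhibitor or beta blocker, not NEB or ZOF specifically.

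Part of the information is already planned. Group means can be approximated by subtraction. Because SAP 3.3 notes that goal attainment at Visit 2 is always zero, the Week 0 to Week 8 shift in goal attainment is visible by group. Neither gives an interval for the mmHg change.

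On the subgroup, a reader might infer that concomitant medication is simply the wrong data source. The wording is ambiguous: it can mean the medication dataset, which holds prior and concomitant records, or the derived category. Under the second reading a drug stopped at Visit 1 is prior, since SAP 6.2 ties study medication to the combination. Replacing the subgroup is unnecessary: it is protocol-listed, and drug class remains identifiable from run-in therapy. That redundancy limits the damage but does not make the ATC rule correct.

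**Conclusion.** Two limited points hold.

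1. The Week 0 to Week 8 change in sitting DBP and SBP is not planned by continued versus switched, although the SAP defines the grouping and uses it for other intervals. Any residual switch response would be included in the primary estimate and could not be examined directly. The illustrative shift of 0.25 to 1.5 mmHg, against the 2 mmHg design margin, rests wholly on assumed shares of 25% to 75% and an assumed residual fall of 1 to 2 mmHg. It could be zero or run the other way. This is a gap in describing the result, not evidence that the primary result is biased.
2. The screening-therapy rule is wrong as written, because it omits patients on other beta-blocker classes. How many is unknown. The data-source wording needs clarifying but is not shown to be an error.

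**What to change.** - **SAP 16.3:** add a descriptive table of the Week 0 to Week 8 change in sitting DBP and SBP for continuers and for switchers in the ITT population, with n, mean, SD and 95% CI. State that it is supportive, carries no test, and does not make continuers a bias-free reference.
- **SAP 7.5:** keep the protocol-listed screening-therapy subgroup. Derive it from the antihypertensive recorded at Visit 1, using all beta-blocker ATC subclasses, and state that medication stopped at Visit 1, classed as prior under SAP 13, is included. As a check, its counts should agree with those for run-in therapy.
- **SAP 3.3:** record the added table as an addition to the protocol analyses.

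The cost is one table and one corrected derivation from data already collected, with no change in sample size. Protocol 14.7 allows SAP modifications to be finalised before database lock. The drawback is the wide intervals shown above, which could be over-read in either direction.

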#### 16.3.2. ANALYSIS OF EXPLORATORY EFFICACY VARIABLES

Exploratory efficacy variables will be summarized in a descriptive manner using safety population for Visits 1, 2 and 3.

- Change in mean sitting SBP and sitting DBP between Visit 1 and Visit 3 will be analyzed as following:
- Change from baseline in sitting SBP and DBP from prior (Visit 1) and post (Visit 3) combination therapy will be compared using paired t-test. The p-value will be presented using a paired t-test comparing mean at baseline and mean at Week 8. The exploratory endpoint will be presented in a descriptive manner using n, mean, median, SD, Q1, Q3, and minimum and maximum. Assumption of normality will be investigated using Wilk-Shapiro test. If violation is observed, then paired t-test will be replaced by Wilcoxon signed rank test.
- The number of patients achieving BP goal (sitting BP ≤130/80 mmHg) will be summarized for Visit 2 and Visit 3, along with percentage. A p-value using exact McNemar's test will be presented to compare the proportion of patients achieving the BP goal (sitting BP ≤130/80 mmHg) between Visit 2 and Visit 3.
- The number of patients achieving BP goal (sitting BP ≤130/80 mmHg) will be summarized for Visit 2 and Visit 3, along with percentage for each of the subgroup specified under section 7.5 of the SAP.

Document: \\ieedc-vnasc01\BIOSdata\Menarini\NebZof\KZA41200\Biostatistics\Documentation\SAP

Author: [name] Version Number: Final V1.0

Version Date: [14Dec2021]

Template No.: CS TP BS016 Revision 6 Reference: CS WI BS005

Page 28 of 37

